13.7.2 Clinical Study Report

A clinical study report (CSR), written in accordance with the ICH E3 Guideline, will be submitted in accordance with local regulations.

3 MODIFICATIONS

3.1 Modifications to the Approved Clinical Study Protocol

Not applicable.

3.2 Modifications to the Approved Statistical Analysis Plan

Not applicable.

3.3 Modifications to the Approved IDMC Charter

Not applicable.

4 INTRODUCTION

This statistical analysis plan (SAP) describes the efficacy and safety analyses and is based on the most recent approved clinical study protocol (CSP), the most recent approved electronic case report form (eCRF), and the most recent approved eCRF completion guidelines. It also documents analyses not specified in the protocol, which will provide supportive information for the scientific understanding of the drug entity.

The Vertex Biometrics Department will perform the statistical analysis of the efficacy and safety data; SAS® Version 9.4 Software (SAS Institute, Cary, North Carolina, USA) or higher will be used to generate all statistical outputs (tables, figures, listings and datasets).

The SAP (Methods) will be finalized and approved before the interim analysis datacut (if applicable) or clinical database lock, whichever occurs earlier. Any revisions to the approved SAP will be documented and approved in an amendment to the SAP prior to the clinical database lock. Any revisions made to the SAP after the clinical database lock will be documented in the clinical study report for this study.

The analysis addressing the pharmacokinetic (PK) objective of the study will be described in the Clinical Pharmacology Analysis Plan (CPAP) which will be developed separately by the Clinical Pharmacology department at Vertex Pharmaceuticals Incorporated (Vertex).

5 STUDY OBJECTIVES

5.1 Part A (Treatment Period)

5.1.1 Primary Objective

- To evaluate the ability of VX-147 to reduce proteinuria

5.1.2 Secondary Objectives

- To evaluate the safety and tolerability of VX-147
- To characterize the PK of VX-147

5.2 Part B

5.2.1 Exploratory Objective

- To evaluate the change proteinuria after stopping administration of VX-147

6 STUDY ENDPOINTS

6.1 Part A

6.1.1 Primary Endpoints

- Percent change from baseline in urine protein to creatinine ratio (UPCR) at Week 13

6.1.2 Secondary Endpoints

- Safety and tolerability based on adverse events (AEs), clinical laboratory values (i.e., hematology, serum chemistry, urinalysis, coagulation studies), standard 12-lead ECGs, and vital signs
- Plasma PK of VX-147

6.1.3 Exploratory Endpoints

- Percent change from baseline in UPCR over time during the Treatment Period
- Percent change from baseline in urine albumin to creatinine ratio (UACR) at Week 13
- Percent change from baseline in UACR over time during the Treatment Period
- Change from baseline in patient-reported outcome (PRO) Short Form Health Survey 36 (SF-36) over time during the Treatment period
- Change from baseline in SF-36 at 4 weeks after the last dose (Safety Follow-up Visit [SFUV])

6.2 Part B (Optional Off-treatment Follow-up Period)

6.2.1 Exploratory Endpoints

- Percent change from baseline in UPCR at the end of the Off-treatment Follow-up Period

7 STUDY DESIGN

7.1 Overall Design

This is a single-arm, open-label, 2-part study. In Part A, all subjects will receive VX-147 at a dosage of 15 mg qd for 2 weeks and VX-147 at a dosage of 45 mg qd for 11 weeks. Part A will be enrolled in 2 cohorts: Cohort 1 and an optional Cohort 2. Cohort 1 includes approximately 10 subjects with UPCR approximately ≥ 3 g/g and < 10 g/g and eGFR approximately ≥ 30 mL/min/1.73 m². Optional Cohort 2 includes approximately 10 subjects with UPCR approximately ≥ 0.8 g/g and < 2.7 g/g and eGFR approximately ≥ 30 mL/min/1.73 m².

[figure not shown]
Subjects in Cohort 1 and Cohort 2 are permitted to take a stable low dose of systemic corticosteroid (prednisone ≤ 10 mg per day or prednisone equivalent) and/or an allowed immunosuppressant (i.e., tacrolimus, mycophenolate, or cyclosporine).

Enrollment of Cohort 1 and Cohort 2 will be managed through the interactive web response system (IWRS).

In Optional Part B, subjects will be followed for up to 12 weeks for evaluation of proteinuria off-treatment (Section 9.1.3 of the CSP).

All subjects will complete a SFUV at 28 (± 7) days after the last dose of study drug.

Figure 7-1 VX19-147-101 Study Design

D: Day; PK: pharmacokinetics; qd: once daily; UPCR: urine protein to creatinine ratio; W: Week

Notes: The figure is not drawn to scale. After completing Part A, subjects will be followed monthly for up to 12 weeks or until UPCR returns to baseline, whichever occurs first. All subjects will be required to complete a SFUV at 28 (± 7) days after the last dose of study drug.

^a Proteinuria will be assessed at multiple timepoints throughout the Treatment Period and Off-treatment Follow-up. Triangles represent timepoints for the primary analysis.

7.2 Sample Size and Power

The sample size was not calculated based on power assumptions, because this is an estimation study. The primary endpoint is percent change from baseline in UPCR at Week 13. Assuming an SD of 0.672 (in log scale), a sample size of 10 subjects will provide a precision of 0.294 (in log scale) for the estimation of the Geometric Mean Percent Change (GMPC) from baseline in UPCR. The precision of the estimate corresponds to the half width of its 80% confidence interval (CI), in log scale.

Table 7-1 displays the expected size of the 80% CIs for the GMPC at various values of the observed GMPC. Approximately 10 subjects will be enrolled in each cohort.

Number of Subjects Completing	Assumption for SD in Log Scale	Observed Geometric Mean (corresponding percent reduction from baseline)			
		0.5 (-50%)	0.6 (-40%)	0.7 (-30%)	0.8 (-20%)
10	0.672	0.37, 0.67 (-63%, -33%)	0.45, 0.81 (-55%, -19%)	0.52, 0.94 (-48%, -6%)	0.60, 1.07 (-40%, 7%)

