12 STATISTICAL AND ANALYTICAL PLANS

This section presents a summary of the planned final analyses for efficacy, safety, and clinical pharmacology. Efficacy and safety statistical analysis details will be provided in the statistical analysis plan (SAP) for this study, and clinical pharmacologic analysis details will be provided in the clinical pharmacology analysis plan (CPAP), both of which will be finalized before last subject last visit for the treatment period (Part A).

The primary endpoint analysis will occur after all subjects in Cohort 1 have completed the SFUV, and all related data have been locked.

An additional analysis for Part A will occur after all subjects in Cohort 2 have completed the SFUV and the related data have been locked.

The final analysis for the study will occur after all subjects have completed their last required visit of the study (Part A or Part B, as applicable) and the database has been locked.

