1 TITLE PAGE

VERTEX PHARMACEUTICALS INCORPORATED

Clinical Study Protocol

A Phase 2a, Open-label, Single-arm, 2-Part Study to Evaluate the Efficacy, Safety, and Pharmacokinetics of VX-147 in Adults With APOL1-mediated Focal Segmental Glomerulosclerosis

Vertex Study Number: VX19-147-101

IND Number:

EudraCT Number: 2020-000185-42

Date of Protocol: 26 July 2021 (Version 6.0)

Replaces Version 5.0 (dated 09 April 2021)

Vertex Pharmaceuticals Incorporated [name]

CONFIDENTIAL

This document contains confidential information. Any use, distribution, or disclosure without the prior written consent of Vertex Pharmaceuticals Incorporated is strictly prohibited except to the extent required under applicable laws or regulations. Persons to whom the information is disclosed must be informed that the information is confidential and may not be further disclosed by them.

Summary of Changes to the Protocol

The previous version of this protocol (Version 5.0, dated 09 April 2021) was amended to create the current version (Version 6.0, 26 July 2021).

Protocol History			
Version and Date of Protocol	Comments		
Version 1.0, 10 October 2019	Original version		
Version 2.0, 05 March 2020	Specified the doses to be used; added optional Cohort 2; modified the schedule of assessments and eligibility criteria.		
Version 3.0, 23 September 2020	Added an option for telemedicine and home health nurse visits to be used during to the Screening Visit; amended the eligibility criteria; several administrative and minor changes.		
Version 4.0, 11 December 2020	Amended the eligibility criteria; specified that both cohorts will be analyzed for the primary endpoint; several administrative and minor changes.		
Version 5.0, 09 April 2021	Modified the eligibility criteria for estimated glomerulofiltration rate (eGFR) and UPCR; updated the study restrictions to allow concomitant use of cyclosporine.		
Version 6.0, 26 July 2021	Current version		

Key changes in the current version of the protocol are summarized below.

Change and Rationale	Affected Sections
Specified that Cohort 1 will enroll "up to 10 subjects" and not "approximately 10 subjects." This change clarifies that enrollment may be stopped before 10 subjects are enrolled.	Sections 2, 9.1, and 12.1

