12.1 Sample Size and Power

The sample size was not calculated based on power assumptions, because this is an estimation study. The primary endpoint is percent change from baseline in UPCR at Week 13. Assuming an SD of 0.672 (in log scale),²⁵ a sample size of 10 subjects will provide a precision of 0.294 (in log scale) for the estimation of the Geometric Mean Percent Change (GMPC) from baseline in UPCR. The precision of the estimate corresponds to the half width of its 80% CI, in log scale. Table 12-1 displays the expected size of the 80% CIs for the GMPC at various values of the observed GMPC. Up to 10 subjects will be enrolled in Cohort 1, and approximately 10 subjects will be enrolled in Cohort 2.

Table 12-1 Two-sided 80% Confidence Interval for GMPC from Baseline in UPCR

Number of Subjects	Assumption for	Observed Geometric Mean (corresponding percent reduction from baseline)			
Completing	SD in Log Scale	0.5 (-50%)	0.6 (-40%)	0.7 (-30%)	0.8 (-20%)
10	0.672	0.37, 0.67 (-63%, -33%)	0.45, 0.81 (-55%, -19%)	0.52, 0.94 (-48%, -6%)	0.60, 1.07 (-40%, 7%)

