9.3.1.2 Analysis of the Primary Efficacy Variable

The primary efficacy endpoint will be analyzed based on combined Cohort 1 and Cohort 2. Subjects non-compliant with study drug will not be included in the analysis.

The primary analysis of the primary efficacy endpoint will be based on the following steps: (1) Log-transform the UPCR values to reduce skewness; (2) Calculate the mean of the change from baseline in log-transformed UPCR, corresponding standard error (SE) and 2-sided 80% CI; (3) The geometric mean and geometric standard error (GSE) will be calculated by back-transforming (exponential-transform) the corresponding estimates obtained in step (2). GMPC from baseline will be obtained as $[\text{geometric mean} - 1] * 100\%$. The corresponding 2-sided 80% CI will be calculated by $[\text{back-transforming (exponential-transform) the CI obtained in step (2)} - 1] * 100\%$.

The GMPC from baseline in UPCR at Week 13, GSE (%), along with the corresponding 2-sided 80% CI will be provided. In addition, the corresponding 2-sided 95% CI will be provided for descriptive purposes.

In addition, the primary efficacy endpoint will also be summarized in a similar way separately for Cohort 1 and Cohort 2.

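### Must the stated precision of 0.294, which is for 10 subjects, be restated because the SAP's primary analysis pools both cohorts?

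*SAP*

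**What the plan says.** SAP 7.2 and section 12.1 of Protocol Version 6.0 carry the same planning statement. The sample size is not based on power because the study is one of estimation. Precision is defined as the half-width of the two-sided 80% confidence interval on the log scale, the SD is taken as 0.672, and "a sample size of 10 subjects will provide a precision of 0.294 (in log scale". The accompanying table (SAP Table 7-1, Protocol Table 12-1) has one row, for 10 completing subjects.

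On cohort size, the Protocol says "Up to 10 subjects will be enrolled in Cohort 1, and approximately 10 subjects will be enrolled in Cohort 2". SAP 7.2 plans about 10 in each cohort, and SAP 7.1 says "Cohort 1 includes approximately 10 subjects with UPCR approximately" 3 g/g or more. Both documents describe Cohort 2 as optional.

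On the analysis, SAP 9.3.1.2 says "The primary efficacy endpoint will be analyzed based on combined Cohort 1 and Cohort 2", with separate cohort summaries in addition. It also says "Subjects non-compliant with study drug will not be included in the analysis". Section 12.3.3 of Protocol Version 6.0 plans separate and combined analyses and does not name one of them as primary.

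**The concern.** Since the study is not sized on power, the expected interval width is its only quantitative efficacy planning figure. That figure is given for 10 subjects, while the analysis the SAP calls primary should have about 20.

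The history suggests how this came about. Protocol Version 2.0 had the same 0.294 and the same row when, in its section 12, "The primary endpoint analysis will occur after all subjects in Cohort 1 have completed the SFUV". The Version 6.0 history records that Version 4.0 "specified that both cohorts will be analyzed for the primary endpoint". The precision text still shows only the 10-completer row.

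There is a worry in the other direction too. Version 6.0 changed the Cohort 1 target to a maximum, and its summary of changes says "This change clarifies that enrollment may be stopped before 10 subjects are enrolled". With exclusions for non-compliance and no imputation of missing data, 0.294 is then the most favourable value for Cohort 1 alone at that SD. A reader could therefore think the pooled result less precise than it should be, and the Cohort 1 result more precise.

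**Working it through.** **Inputs.** SD 0.672, n = 10 and the two-sided 80% level come from SAP 7.2 and Protocol 12.1. The pooled size of about 20 is 10 + 10 from the same sections. Neither document gives a dropout or non-compliance rate, so every other n below is an assumption for illustration.

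**Formula.** The estimator is a simple mean of log changes, so half-width = t(0.90, n−1) × SD / √n. Limits on the ratio scale are the observed geometric mean × exp(± half-width).

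**The plan's own figure.** n = 10: 1.3830 × 0.672 / √10 = 1.3830 × 0.2125 = 0.2939, which is the stated 0.294. A normal quantile would give 0.272, so the plan used the t distribution. With 0.294, observed ratios of 0.5, 0.6, 0.7 and 0.8 give 0.373–0.671, 0.447–0.805, 0.522–0.939 and 0.596–1.073. These agree with the table to its rounding.

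**The pooled set at the same SD.**

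| Evaluable n | t × SD/√n | Half-width | Upper limit at observed 0.8 |
|---|---|---|---|
| 10 (as tabulated) | 1.3830 × 0.2125 | 0.294 | 1.07 (+7%) |
| 16 | 1.3406 × 0.1680 | 0.225 | 1.002 (about 0%) |
| 18 | 1.3334 × 0.1584 | 0.211 | 0.988 (−1%) |
| 20 | 1.3277 × 0.1503 | 0.200 | 0.977 (−2%) |

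Ratios of stated to pooled half-width: 0.2939/0.1995 = 1.47 at n = 20, and 0.2939/0.2252 = 1.31 at n = 16. The half-width falls as n rises, so at this SD any pooled set of more than 10 has a narrower expected interval than the one stated. At n = 12 it is already 0.264.

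**How large an SD would remove the margin.** Solving for SD: 0.294 × √20 / 1.3277 = 0.990 at n = 20, and 0.294 × √16 / 1.3406 = 0.877 at n = 16.

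**Different mean changes in the two cohorts.** With 10 per cohort and a difference d in mean log change, the expected pooled variance is about 0.672² + (d/2)² × 20/19. For an assumed d of 0.3 this is 0.4516 + 0.0237 = 0.4753 (SD 0.689, half-width 0.205). For an assumed d of 0.5 it is 0.4516 + 0.0658 = 0.5174 (SD 0.719, half-width 0.214). Both stay well below 0.294.

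**Cohort 1 below 10.** n = 9 gives 1.3968 × 0.2240 = 0.313, and n = 8 gives 1.4149 × 0.2376 = 0.336. At an observed 0.7 the upper limits are 0.96 and 0.98, against 0.94 at n = 10. At n = 7 (1.4398 × 0.2540 = 0.366) the limit reaches 1.01.

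**The case for a change.** The best case for amending the text is that an estimation study should state the expected precision of the analysis it calls primary, and that the reading does shift. At an observed 20% reduction the tabulated interval includes no change, whereas the pooled interval at 18 or 20 subjects excludes it. The single row also says nothing about a Cohort 1 that stops short of 10. The remedy would be cheap: a label and a few rows.

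What stands is that a combined precision is nowhere stated and that the row is not labelled per cohort. Neither misleads in practice. The sentence and the table column both tie the figure to 10 subjects, and the cohort sizes are in the same section, so the per-cohort reading is plain. The separate cohort summaries are planned in their own right, and the row describes them. If optional Cohort 2 were not enrolled, the combined set would be Cohort 1, and the row would describe the primary analysis at 10 completers.

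The shift at a 20% reduction has no consequence under the plan, because no decision is attached to whether the interval excludes zero change. The reported interval will use the observed SD and n in any case. A smaller Cohort 1 will show its own wider interval; the stated figure makes no promise for fewer than 10.

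The mismatch lies mainly in the SAP. Protocol Version 6.0 does not name the pooled analysis as primary, and its Version 4.0 history line says both cohorts will be analysed, not that they will be pooled. As for the Cohort 1 wording, Version 6.0 records that approximately 10 was the previous text. The available copy of the SAP shows no date, so it may simply match the earlier protocol.

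**Conclusion.** No change is needed. The 0.294 and its table are correct for what they describe, one cohort with 10 completers. The missing combined figure is an omission in the conservative direction: the expected half-width is 0.200 with 20 evaluable subjects, or 0.225 with 16, against 0.294 stated. An analyst following the plan as written obtains the same estimate, interval and conclusion whether or not a combined row is printed.

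This rests on three assumptions: that optional Cohort 2 is enrolled, that more than 10 subjects are evaluable in the combined set, and that an SD near 0.672 holds across the two UPCR ranges. The last has a wide margin, since the pooled SD would have to reach about 0.99 (n = 20) or 0.88 (n = 16) before the stated figure ceased to be cautious. If Cohort 2 were not enrolled and Cohort 1 fell short of 10, the figure would be mildly optimistic (0.313 at 9, 0.336 at 8), which its explicit condition of 10 subjects already makes visible. The cohort-size wording in the SAP is at most clerical.

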7.3 Randomization

This is an open-label study. Randomization is not required because all subjects will receive VX-147.

7.4 Blinding and Unblinding

This is an open-label study. Refer to Section 10.7 of CSP for details.

8 ANALYSIS SETS

The following analysis sets are defined: All Subjects Set, Full Analysis Set (FAS), Follow-up Set and Safety Set.

8.1 All Subjects Set

The **All Subjects Set** will include all subjects who were enrolled in the study. This analysis set will be used for all individual subject data listings and disposition summary tables, unless otherwise specified.

8.2 Full Analysis Set

The **Full Analysis Set (FAS)** will include all subjects who received at least 1 dose of study drug in the Treatment Period and with at least 1 post-baseline efficacy assessment. The FAS will be used to summarize subject demographics and baseline characteristics, and for all efficacy analyses in the Treatment Period, unless otherwise specified.

8.3 Follow-up Set

The **Follow-up Set** will include all subjects who entered the Off-treatment Follow-up Period (Part B) and have at least 1 efficacy assessment in that period. The Follow-up Set will be used for all efficacy analyses in the Off-treatment Follow-up Period, unless otherwise specified.

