Study Duration Excluding the Screening Period, each subject will participate in the study for

approximately 13 weeks of treatment in Part A. Subjects may choose to participate in an off-treatment observation for up to 12 weeks in Part B (optional). All subjects will

complete a SFUV at 28 (\pm 7) days after the last dose of study drug.

Study Design This is a single-arm, open-label, 2-part study. In Part A, subjects will receive VX-147

at a dosage of 15 mg once daily (qd) for 2 weeks and VX-147 at a dosage of 45 mg qd for 11 weeks. Part A will be enrolled in 2 cohorts: Cohort 1 and optional Cohort 2. Cohort 1 includes up to 10 subjects with UPCR approximately \geq 3 g/g and <10 g/g and eGFR approximately \geq 30 mL/min/1.73 m². Optional Cohort 2 includes approximately 10 subjects with UPCR approximately \geq 0.8 g/g and <2.7 g/g and eGFR approximately

 \geq 30 mL/min/1.73 m².

Subjects in Cohort 1 and Cohort 2 are permitted to take a stable low dose of systemic corticosteroid (prednisone ≤ 10 mg per day or prednisone equivalent) and/or an allowed immunosuppressant (i.e., tacrolimus, mycophenolate, or cyclosporine).

[figure not shown]
Enrollment of Cohort 1 and Cohort 2 will be managed through the interactive web

response system (IWRS).

After completing Part A, subjects will be followed for up to 12 weeks in Part B (optional) for evaluation of proteinuria off treatment if they consent to do so. If a subject prematurely discontinues study drug in Part A, an Early Treatment Termination (ETT) Visit should be scheduled as soon as possible after the decision to terminate study drug treatment. After completing the ETT Visit, subjects will not complete further Part A Visits; these subjects will come in for a SFUV and will not continue to Part B

All subjects are required to complete a SFUV at 28 (\pm 7) days after the last dose of study drug. The SFUV may occur while a subject is participating in Part B.

Figure 2-1 VX19-147-101 Study Design

D: Day; PK: pharmacokinetics; qd: once daily; UPCR: urine protein to creatinine ratio; W: Week

Notes: The figure is not drawn to scale. After completing Part A, subjects will be followed monthly for up to 12 weeks or until UPCR returns to baseline, whichever occurs first. All subjects will be required to complete a SFUV at 28 (\pm 7) days after the last dose of study drug.

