Standard 12-lead ECG		X		Complete after SF-36 and before other assessments after subject has been supine for at least 5 minutes. ECGs (Section 11.6.4), vital signs, and blood draws should be performed in said order.
Vital signs		X		Complete before other assessments listed below after subject has been at rest for at least 5 minutes; they should be seated during the assessment (Section 11.6.3). Blood pressure will be collected in triplicate.

^a The postdose PK sampling visit is required for all subjects, with the exception of those who complete an ETT Visit.

The SFUV and Part B Week 4 Off-treatment Follow-up Visit may occur on the same day, provided the visit windows are met for both visits.

Visit windows for Part B are as follows: Week 4 Visit (Day 120 ± 2 weeks), Week 8 Visit (Day 148 ± 2 weeks), Week 12 Visit (Day 176 ± 2 weeks).

Table 3-3 Study VX19-147-101: Postdose PK Sampling, Safety Follow-up Visit, and Part B Off-treatment Follow-up Period

On-treatment Follow-up reriou					
Event/Assessment	Postdose PK Sampling (Approximately 48 hours after the last dose of study drug) ^a	SFUV 28 (± 7) Days After Last Dose of Study Drug ^b	Part B: Optional Off-treatment Follow-up Visits (Part B Week 4 ^b , 8, and 12)	Comments	
Weight		X		Weight will be measured with shoes off and light weight closing (no outerwear). (Section 11.1).	
Abbreviated physical examination		X		In addition to the scheduled visits, symptom-directed physical examinations will occur at any time during the study if triggered by AEs or if deemed necessary by the investigator (Section 11.6.3).	
Serum chemistry		X Fasted		A blood sample will be collected following an overnight fast (Section 11.6.2).	
Hematology		X		A blood sample will be collected (Section 11.6.2)	
Coagulation		X		A blood sample will be collected (Section 11.6.2)	
VX-147 PK Sampling	X			A blood sample will be collected (Section 11.2.1).	
Urine sample		X	X	The first morning urine void will be collected and used for efficacy, safety, and biomarker analyses (Sections 11.3 and 11.6.2). Refer to sample handling guidelines to ensure samples are collected and submitted appropriately for analysis.	
β-hCG (urine)		X		All female subjects of childbearing potential (Section 11.6.2). This can be collected in the same sample as the other urine sample.	
Adverse events		gning of ICF through UV	NA	Section 11.6.1	

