6.2 Part B

6.2.1 Exploratory Objective

• To evaluate the change proteinuria after stopping administration of VX-147

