9.1.2.3 Early Termination of Treatment or Early Discontinuation

If a subject prematurely discontinues study treatment, an Early Termination of Treatment (ETT) Visit should be scheduled as soon as possible after the subject decides to terminate study treatment. Subjects who prematurely discontinue treatment will also be required to complete the SFUV, approximately $28 (\pm 7)$ days after their last dose of study drug. The assessments performed at the SFUV are listed in Table 3-3.

If the ETT Visit occurs 3 weeks or later following the last dose of study drug, then the ETT Visit will replace the SFUV, and a separate SFUV will not be required.

After the ETT Visit, subjects will not complete further Part A Visits; these subjects will not continue to Part B.

If a subject withdraws consent for the study, no further assessments will be performed. Vertex may retain and continue to use any data and samples collected before such withdrawal of consent.

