9.1.3 Part B

Participation in Part B is optional. After the last Part A Visit, subjects will be followed off-treatment at a visit scheduled every 4 weeks (\pm 2 weeks) to assess the change in proteinuria after stopping administration of VX-147 (Table 3-3). Part B visits will continue until the UPCR level reaches \geq 90% of baseline levels or 3 months after the last dose of study drug, whichever occurs first. If a subject has not achieved \geq 90% of baseline UPCR by the Part B Week 12 Visit, the Part B Week 12 Visit will be the last study visit.

Subjects will not be allowed to participate in Part B if (1) their UPCR level during Part A remained \geq 90% of baseline or (2) their UPCR level reached \geq 90% of baseline before the Part A Week 13 Visit and remained at that level through the Week 13 Visit.

The SFUV and Part B Week 4 Off-treatment Follow-up Visit may occur on the same day, provided the visit windows for both visits are met.

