9.3 Efficacy Analysis

Efficacy analyses for Treatment Period (Part A) will be based on FAS and efficacy analyses for Off-treatment Follow-up Period (Part B) will be based on Follow-up Set, unless specified

otherwise. All efficacy analyses will be conducted separately for Cohort 1 and Cohort 2, as well as combined.

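### Off-treatment UPCR is summarised only in Part B entrants, a volunteer set restricted by on-treatment UPCR, although the SFUV void would allow a 4-week off-treatment summary in all Part A completers

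*SAP*

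**What the plan says.** The references are to Protocol Version 6.0 and the SAP.

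- **Objective.** Protocol 6.2.1 gives the Part B exploratory objective as "To evaluate the change proteinuria after stopping administration of VX-147". The endpoint in Protocol 7.2.1 is percent change from baseline in UPCR at the end of the off-treatment period.
- **Entry to Part B.** Protocol 9.1.3 states "Participation in Part B is optional". It bars subjects whose UPCR stayed at or above 90% of baseline during Part A. It also bars them if "their UPCR level reached \geq 90% of baseline before the Part A Week 13 Visit and remained at that level through the Week 13 Visit". Early discontinuers do not continue to Part B (Protocol 9.1.2.3).
- **Analysis set.** SAP 8.3 says the Follow-up Set "will include all subjects who entered the Off-treatment Follow-up Period (Part B) and have at least 1 efficacy assessment in that period". SAP 9.3 says efficacy analyses for "Off-treatment Follow-up Period (Part B) will be based on Follow-up Set".
- **Time points.** SAP 9.3.2.2 gives off-treatment GMPC at Part B Weeks 4, 8 and 12. The treatment-period UPCR summaries end at Week 13. SAP Appendix A, Table 12-1, has no Safety Follow-up row for UPCR.
- **SFUV sample.** The Protocol synopsis says "All subjects are required to complete a SFUV at 28" (±7) days after the last dose. Protocol Table 3-3 marks a urine sample at the SFUV and at the Part B visits, with one comment covering both: "The first morning urine void will be collected and used for efficacy, safety, and biomarker analyses". There is one exception: "If the ETT Visit occurs 3 weeks or later following the last dose of study drug, then the ETT Visit will replace the SFUV".

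**The concern.** Membership of the Follow-up Set depends partly on the variable being summarised. The bar removes subjects with persistently high on-treatment UPCR. A subject's deviations from the average are likely to be correlated over time, so those who remain would tend to have lower UPCR after stopping as well, whether or not any drug effect persists. Consent adds a second, unmeasured selection.

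There is no control arm, so the off-treatment course is the only withdrawal evidence in the study, and the SAP plans confidence intervals and a figure for it. A residual reduction at Part B Week 4 could therefore be partly a product of who was allowed in. The SFUV void, taken at about the same time off drug in subjects outside Part B as well, enters no planned UPCR summary.

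**Working it through.** **1. The plan's own figure.** SAP 7.2 gives SD 0.672 on the log scale, n = 10 and a precision of 0.294. The half-width is t(0.90, 9 df) × SD/√n = 1.383 × 0.672/√10 = 0.294. It reproduces, and the SD is used below.

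**2. Does the SFUV fall in the Part B Week 4 window?** The Week 13 Visit is Day 92 (-2 days), and the last dose is the day before it (Protocol Table 3-2), so the last dose is on Day 89 to 91.
- Earliest SFUV: 89 + 21 = Day 110.
- Latest SFUV: 91 + 35 = Day 126.

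The Part B Week 4 window for UPCR is (106, 134], so a completer's SFUV lies wholly inside it. Table 12-1 windows are applied by study day. An entrant's SFUV void could therefore supply the Part B Week 4 value, while the same void from a non-entrant is excluded by the Follow-up Set definition.

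**3. The entry rule.** On scheduled visits, each of the two bars requires UPCR at or above 90% of baseline at Week 13 and at least at the visit before it, Week 9. A subject below 90% at Week 9 who first reaches 90% at Week 13 is not barred. The rule modelled is therefore: barred if Week 9 and Week 13 are both at or above 90% of baseline.

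**4. Size of the selection effect (illustrative).** None of these assumptions except the SD comes from the documents:
- log changes at Week 9, Week 13 and Part B Week 4 are jointly normal, each with SD 0.672;
- Week 9 and Week 13 have the same mean, ln(GM), where GM is the geometric mean ratio to baseline;
- the true mean off-drug change is zero (full return to baseline);
- the Week 9/Week 13 correlation r is 0.5 to 0.85;
- the off-drug change has correlation ρ of 0.3 to 0.7 with both visits;
- all eligible subjects enter.

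Let c = (ln 0.9 − ln GM)/0.672, and let P be the probability that both standardised changes are at or above c. Then

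mean off-drug log change in entrants = −0.672 × 2ρ φ(c) Φ(−c√((1−r)/(1+r))) / (1 − P).

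Worked case, with GM 0.7, r 0.7 and ρ 0.5:
- c = 0.374, φ(c) = 0.372, Φ(−0.157) = 0.438 and P = 0.237.
- Mean = −0.672 × (2 × 0.5 × 0.372 × 0.438)/0.763 = −0.143.
- exp(−0.143) − 1 = −13.4%.

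| Week 13 GMPC | Eligible for Part B | Part B Week 4 GMPC when the truth is 0% |
|---|---|---|
| -30% | 73% to 80% | -7.5% to -19.7% |
| -40% | 80% to 86% | -5.5% to -15.5% |
| -50% | 87% to 92% | -3.6% to -11.2% |

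The smaller effect in each row is at r 0.5 and ρ 0.3, the larger at r 0.85 and ρ 0.7.

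**5. A check without correlations.** Suppose 20 subjects complete, 4 do not enter and are at 100% of baseline off drug, and the 16 entrants have a GMPC of -30%. Over all 20, the ratio is 0.7^(16/20) = 0.752, which is -25%.

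**The case against.** The restriction is deliberate and explained. The Protocol Version 2.0 summary of changes reasons that a subject already back at baseline has no return to baseline to follow. The objective and endpoint belong to Part B, the SAP says openly who is in the Follow-up Set, and the study is a small estimation study without hypothesis tests. All of that stands. It justifies not following these subjects for 12 weeks, but it does not explain leaving their SFUV value out of any summary.

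Four stronger readings are tempting, and the documents do not support them.

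- *Entry requires a Week 13 value below 90% of baseline.* Under that rule, with a Week 13 GMPC of -30%, about 65% would qualify and the spurious reduction would be -11% to -24%. Protocol 9.1.3 is narrower (step 3), so those figures are too large.
- *The SFUV sample is collected and then unused.* Individual data listings cover the All Subjects Set (SAP 8.1), and urinalysis results are listed (SAP 9.4.2). What is missing is a summary. The efficacy label is also one comment shared by the SFUV and Part B columns.
- *The plan offers Part B as the off-drug result for all treated subjects.* No section says so. The risk lies in how an unlabelled table would be read.
- *The SFUV value is free of selection and should be the main off-treatment result.* A completer summary still omits early discontinuers, and it rests on a single void. Which summary leads is a matter of preference.

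**Conclusion.** The point holds as a minor one. Off-treatment UPCR is summarised only in a self-selected set restricted by on-treatment UPCR. With any positive correlation between on-drug and off-drug change, the Part B Week 4 GMPC is expected to overstate the residual reduction relative to all Part A completers, provided consent does not select in the opposite direction.

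The documents give neither the correlations, the off-drug SD nor the entry rate, so the size cannot be determined. Under the stated assumptions the reading would be about -7% to -20% at a Week 13 GMPC of -30%, -6% to -16% at -40% and -4% to -11% at -50%, where the truth is 0%. The stronger the drug effect, the fewer subjects are barred and the smaller the distortion. The endpoint is exploratory, and the Week 13 primary result is unaffected.

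**What to change.** In SAP 9.3.2.2 and Appendix A, Table 12-1, add a supplementary GMPC summary of UPCR at about 4 weeks off treatment.

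- **Population:** all Full Analysis Set subjects who completed Part A dosing, by cohort and combined.
- **Value:** the nominal SFUV void. Use the Part B Week 4 void only if no SFUV void is available. This settles which sample counts when the two visits are on different days.
- **Presentation:** beside the Part B Week 4, 8 and 12 summaries, with those labelled as conditional on Part B entry.

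The cost is one SAP paragraph, one visit row and one table. No new visit or sample is needed, because urine protein and creatinine are already in the urine panel. The limits are that the value is a single void taken 21 to 35 days after the last dose, and that early discontinuers are still not covered.
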